Study Objectives	 Primary objective: To assess the anti-tumor activity of Tenalisib as determined by the objective response rate (ORR) and duration of response (DoR) Secondary objectives: 		
	 To characterize safety and tolerability of Tenalisib. To assess progression free survival (PFS) 		
End points	 Efficacy: Overall response rate (ORR): ORR is defined as sum of complete response (CR) and partial response (PR) rates as defined by iwCLL guideline for CLL (Hallek et al. 2018). Duration of response (DoR): DoR is defined as the interval from the first documentation of CR/PR to first documentation of definitive disease progression or death from any cause. Progression-free survival (PFS): PFS is defined as the interval from first dose to first documentation of definitive disease progression or death from any cause. 		
	Safety: • Adverse Event (AE), Grade 3/4 AEs, Serious Adverse Event (SAE).		
Study Design and procedure	The trial is a Phase II, open label, Simon's two stage study design to evaluate the efficacy and safety of Tenalisib in 61 patients with CLL who have relapsed or are refractory after at least one prior therapy. In stage 1, 20 patients will be enrolled. If eight or fewer responders are observed at this stage, the study will be terminated. Else, 41 additional patients will be enrolled into stage 2. The study treatment Tenalisib (800 mg BID) will be administered orally in 28-		
	days of cycle over a period of 7 months (C1D1 to C8D1) in absence of definitive disease progression or unacceptable toxicity. The study will end when all ongoing subjects have reached their third tumor assessment on Cycle 8/Day 1 (C8D1) or have discontinued from the study for any reason, whichever is earlier. At the end of the study, all ongoing patients with no evident disease progression will be given an opportunity to enroll in an open-label compassionate medication use study [Protocol:RP6530-1803; NCT03711604] and will be followed up. The detailed study procedure is presented in Study assessment and Treatment schedule (Table 1). Anti-infective prophylaxis (e.g.		

CONFIDENTIAL Page 5 of 61

Version: 1.0, Dated 12 September 2019

	for herpes simplex virus (HSV), pneumocyctis Jirovecii pneumonia (PJP), hepatitis B virus (HBV), cytomegalovirus (CMV) are recommeded and will be	
	given at the discretion of study investigator. All safety laboratory assessments,	
	electrocardiogram (ECG) and radiological assessments (e.g. CT) will be	

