
CONFIDENTIAL Page 8 of 61 Protocol No: RP6530-1901 Version: 1.0, Dated 12 September 2019

version: 1.0, Dated 12 Se	ptember 2019
	 Herbal medications. Patients should stop using herbal medications at least 7 days prior to C1D1. Strong inhibitors or inducers of CYP3A4. Patients should stop using these medications at least 7 days or 5 half-lives (whichever is shorter) prior to C1D1. Strong inhibitors or inducers of CYP2C9. Patients should stop using these medications at least 7 days or 5 half-lives (whichever is shorter) prior to C1D1. Substrates of CYP3A4 enzyme with a narrow therapeutic range. Patients should stop using these medications at least 7 days or 5 half-lives (whichever is shorter) prior to C1D1. Use of heparin, warfarin, apixaban or rivaroxaban for prophylaxis and/or treatment of venous thrombosis is prohibited. These drugs should be stopped at least 7 days or 5 half-lives (whichever is shorter) prior to C1D1. Live attenuated vaccine (e.g. Flu vaccine, pneumovax, varicella) Steroids > 20 mg unless it is required for management of toxicity (e.g., transaminitis) during the study.
Estimated Study	Approximately 10-12 months for patient accrual plus 7.5 months of treatment
duration	and follow up. Estimated clinical duration is about 20 months.
Response assessment	Efficacy will be evaluated by CT scan at C3D1±7 days, C5D1±7 days and C8D1±7 days or at End of the treatment (EOT) visit. The determination of response and progression will be based on iwCLL guidelines for diagnosis and treatment of CLL (Hallek et al. 2018). Unilateral bone marrow aspiration and/or biopsy will be performed at investigator discretion in patients for whom assessment of extent of CLL involvement and bone marrow cellularity is important in determining eligibility. However, bone marrow biopsy should be done to confirm potential CR. Radiographic and clinical tumor response as evaluated and confirmed by the site investigator (defined as PI-confirmed response) will be considered for
Cample des	analyses of ORR and other efficacy endpoints.

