Sample size	The sample size is derived based on Simon's two stage design to achieve 90% power at alpha of 0.05 for the null hypothesis of $ORR \le 40\%$, assuming 60% response rate. Up to 61 patients will be enrolled. In stage 1, 20 patients will be enrolled. If eight or fewer responders are observed in this stage, the study will be terminated without rejecting the null hypothesis. Else, 41 additional patients will be enrolled into stage 2. If 31 or more responders are observed in the study, the null hypothesis of $ORR \le 40\%$ will be rejected.
Statistical Analysis	Statistical methods to analyze efficacy and safety will be described in statistical analysis plan (SAP). These methods may be revised and updated due to reasons such as regulatory requirements or need for further clarifications. The final analysis plan will be documented in a formal SAP that will be

CONFIDENTIAL Page 9 of 61

Protocol No: RP6530-1901 Rhizen Pharmaceuticals S.A.

Version: 1.0, Dated 12 September 2019

finalized before database lock. The SAP will include details on how variables will be derived, how missing data will be handled, and how data will be presented as well as the details on statistical methods to be used for safety and efficacy analyses. The final clinical study report will discuss deviations from the SAP, if any.

CONFIDENTIAL Page 10 of 61

Protocol No: RP6530-1901 Version: 1.0, Dated 12 September 2019

GENERAL INFORMATION			
SPONSOR			
SPONSOR'S REPRESENTATIVE			
SPONSOR'S MEDICAL EXPERT			
STATISTICIAN			

CONFIDENTIAL Page 11 of 61

Version: 1.0, Dated 12 September 2019

List of Abbreviations

ΑE Adverse Event ALP Alkaline Phosphatase Alanine aminotransferase ALT (SGOT) ANC Absolute Neutrophil Count

aPTT Activated Partial Thromboplastin Time

Allo-SCT Allogeneic Hematopoietic Stem Cell Transplantation Autologous Hematopoietic Stem Cell Transplantation Auto-SCT

AST (SGPT) Aspartate aminotransferase

AUC Area Under the plasma-concentration time curve

BID Twice Daily

β-HCG β-human chorionic gonadotropin Peak Drug Concentration C_{max} Complete Blood Count **CBC** Code of Federal Regulation **CFR**

Cytomegalovirus **CMV**

Chronic Lymphocytic Leukemia CLL Central Nervous System CNS CR Complete Response CRF Case Report Form CrCl Creatinine Clearance

Computed Tomography CT**CTCAE** Common Terminology Criteria for Adverse Events

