3.2 Design of Trial

The trial is a Phase II, open label, Simon's two stage study design to evaluate the efficacy and safety of Tenalisib in 61 patients with CLL who have relapsed or are refractory after at least one prior therapy. In Stage 1, 20 patients will be enrolled and the study treatment Tenalisib (800 mg BID) will be administered orally in 28-days of cycle over a period of 7 months (C1D1 to C8D1) in absence of definitive disease progression or unacceptable toxicity. If 8 or fewer responders are observed in this stage, the study will be terminated. Else, 41 additional patients will be enrolled into stage 2.

Patients will be evaluated for efficacy response by CT at C3D1±7 days, C5D1±7 days and C8D1±7 days and/or at End of the treatment (EOT) visit. The study will end when all ongoing subjects have reached their third tumor assessment on Cycle 8/Day 1 (C8D1) or have discontinued from the study for any reason, whichever is earlier. At the end of the study, all ongoing patients with no evident disease progression will be given the opportunity to enroll in an open-label compassionate medication use study [Protocol:RP6530-1803; NCT03711604] and will be followed up. The details of the study procedures are given in Study Assessments and Treatment Schedule (*Table 1*).

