The Expected Duration of Subject Participation and Follow-up

The expected duration of subject participation in the study is 7 months (C1D1 to C8D1). The study will end when all ongoing subjects have reached their third tumor assessment on Cycle 8/Day 1 (C8D1) or have discontinued from the study for any reason, whichever is earlier. At the end of the study, all ongoing patients with no evident disease progression will be given the opportunity to enroll in an open-label compassionate medication use study [Protocol:RP6530-1803] and will be followed up.

Study Stopping Rules

The following study stopping rules based on the safety and efficacy will be used.

Safety: The DRC will continue to monitor safety of Tenalisib (or toxicity trends that may be of concern) at interval of approximately 3 months from initiation of study until the completion of the study. In the event of one (1) death attributed to the study drug,

Version: 1.0, Dated 12 September 2019

study accrual will be suspended pending further investigation, and will only be resumed at the recommendation of the DRC. In addition, the DRC may recommend for termination of the study in case of major safety concerns.

• Efficacy: Once 20 patients are recruited in stage 1 of the study, the DRC will review the efficacy results and may recommend early termination of the study if there are 8 or fewer responders out of 20 patients. Else, 41 additional patients will be enrolled into stage 2.

In addition, Sponsor reserves the right to terminate the study in the interest of patient safety, for noncompliance with the protocol, lack of recruitment or any other administrative reasons. The sponsor and PIs will notify the regulatory authority and respective IRB/IEC respectively if the trial terminates early, with a justification for the early termination.

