9 STATISTICAL METHOD AND CONSIDERATIONS

This section describes the statistical methods to be used to analyze efficacy and safety. These methods may be revised and updated due to reasons such as regulatory requirements or need for further clarifications. The final analysis plan will be documented in a formal statistical analysis plan (SAP) that must be finalized before database lock. The SAP will include details on how variables will be derived, how missing data will be handled, and how data will be presented as well as the details on statistical methods to be used for safety and efficacy analyses. The final clinical study report will discuss deviations from the SAP, if any.

9.1 **General Considerations**

Unless otherwise stated, all statistical analyses will be performed using a two-sided hypothesis test at the overall 5% level of significance. Continuous data will be described using the following descriptive statistics: n, mean, median, minimum and maximum. Data will be displayed in all listings sorted by phase, group and patient number.

When count data are presented, the percentage will be suppressed when the count is zero in order to draw attention to the non-zero counts. A row denoted "Missing" will be included in count tabulations where necessary to account for dropouts and missing values. Unless otherwise specified, the denominator for percentages will be the number of patients with a non-missing assessment in a given treatment group within the analysis population of interest.

All statistical analyses will be performed using SAS 9.1 or higher.

Determination of Sample Size

The sample size is derived based on Simon's two stage design to achieve 90% power at alpha of 0.05 for the null hypothesis of ORR \(\le 40\%,\) assuming 60\% response rate. Up to 61 patients will be enrolled. In stage 1, 20 patients will be enrolled, if 08 or fewer responders are observed in this stage, the study will be terminated without rejecting the null hypothesis. Otherwise, 41 additional

CONFIDENTIAL Page 50 of 61

^{*}Sum of the products of 6 or fewer lymph nodes (as evaluated by CT scans and physical examination). No increase in any lymph node and no new enlarged lymph node (diameter ≥ 1.5 cm). For small lymph nodes (longest diameter < 1.5cm), an increase <25% is not considered significant.

Version: 1.0, Dated 12 September 2019

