5.1 Study Stopping Rules

- **Safety:** *The Data review Committee (DRC) will continue to monitor safety of Tenalisib (or toxicity trends that may be of concern) at interval of approximately 3 months from initiation of study until the completion of the study. In the event of one (1) death attributed to the study drug, study accrual will be suspended pending further investigation, and will only be resumed at the recommendation of the DRC. In addition, the DRC may recommend for termination of the study in case of major safety concerns.*
- **Efficacy:** *Once 20 patients are recruited in stage 1 of the study, the DRC will review the efficacy results and may recommend early termination of the study if there are 8 or fewer responders out of 20 patients. Else, 41 additional patients will be enrolled into stage 2.*

In addition, Sponsor reserves the right to terminate the study in the interest of patient safety, for noncompliance with the protocol, lack of recruitment or any other administrative reasons. The sponsor and PIs will notify the regulatory authority and respective IRB/IEC respectively if the trial terminates early, with a justification for the early termination.

Notes:

- After reviewing the efficacy data, the study has been closed due to absence of clinically meaningful response to single agent Tenalisib in Stage 1 of the study. Therefore, Stage 2 will not be performed.
- The analysis proposed in this SAP is considering the available data at the time of completion of the study.

6. Sample Size Considerations

The sample size was derived based on Simon's two stage design to achieve 90% power at alpha of 0.05 for the null hypothesis of $ORR \leq 40\%$, assuming 60% response rate. Up to 61 patients will be enrolled. In stage 1, 20 patients will be enrolled, if 08 or fewer responders are observed in this stage, the study will be terminated without rejecting the null hypothesis. Otherwise, 41 additional patients will be enrolled into stage 2. If 31 or more responders are observed in the study, the null hypothesis of $ORR \leq 40\%$ will be rejected.

Stage 1: 21 patients with relapsed/refractory CLL is enrolled.

Stage 2 will not be initiated as the study is closed due to absence of clinically meaningful response to single agent Tenalisib.

7. Analysis Populations**7.1 Modified Intent-to-Treat Population (mITT) Analysis Set**

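### The stage 1 stop is mandatory in seven places but discretionary in the two Study Stopping Rules sections, which also tie the look to recruitment, not assessment

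*Protocol*

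**What the plan says.** The stop at 8 or fewer responders among 20 stage 1 patients is stated nine times across the two documents.

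**Mandatory, seven places.**
- Protocol synopsis, Study Design: "If eight or fewer responders are observed at this stage, the study will be terminated".
- Protocol synopsis, Sample size: "If eight or fewer responders are observed in this stage, the study will be terminated without rejecting the null hypothesis". SAP 9.1 repeats this.
- Protocol 3.2: "If 8 or fewer responders are observed in this stage, the study will be terminated". SAP 5 repeats this.
- Protocol 9.2: "if 08 or fewer responders are observed in this stage, the study will be terminated without rejecting the null hypothesis". SAP 6 repeats this.

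**Discretionary, two places.** Protocol 3.7 (Study Stopping Rules) reads "Once 20 patients are recruited in stage 1 of the study, the DRC will review the efficacy results and may recommend early termination". SAP 5.1 has the same sentence, in which the committee "may recommend early termination of the study if there are 8 or fewer responders out of 20 patients". In both, the next sentence sends the trial to stage 2 otherwise.

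These two sections are also the only ones that time the review, and they time it by recruitment. Neither names a response assessment or says whether accrual pauses. SAP 9.2 states that there is no formal interim analysis and refers the reader to SAP 5.1 for detail.

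**The concern.** The alpha and power of a two-stage design belong to one specific rule: who is counted at the look, and what happens at each count. The documents give two versions of that rule, and the sections a review committee would open first carry the looser one.

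Two things are at stake. First, if stopping is optional, some trials that should have ended at stage 1 go on and may reject at the end, which adds to the type I error. Second, if the look is taken when the 20th patient is recruited, many of the 20 will not yet have had a scan. The boundary of 8 is defined only for 20 patients, so the committee would have to improvise, and an improvised look on fewer patients can stop an active drug more often than planned.

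**Working it through.** **Inputs.** Null ORR 40%, alternative 60%, stage 1 n = 20 with a stop at 8 or fewer, total 61, rejection at 31 or more (Protocol 9.2, SAP 6 and 9.1). First response CT at C3D1, study day 57, so 56 days after first dose, with a window of 7 days either way (Protocol 3.2 and Table 1). Accrual from the synopsis: "Approximately 10-12 months for patient accrual plus 7.5 months of treatment".

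**Step 1: reproduce the plan's figures.** With a binding stop and all 20 assessed,

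P(reject | p) = sum over x = 9 to 20 of P(Bin(20, p) = x) × P(Bin(41, p) ≥ 31 − x).

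- p = 0.40: 0.0487, within the stated 0.05 (one-sided).
- p = 0.60: 0.904, matching the stated 90%.
- Chance of stopping at stage 1: 0.596 at 40% and 0.057 at 60%.

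The sample-size arithmetic is correct.

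**Step 2: treat the stop as optional.**
- Never enforced: alpha = P(Bin(61, 0.40) ≥ 31) = 0.0565; power = P(Bin(61, 0.60) ≥ 31) = 0.943.
- Overridden only at exactly 8 of 20, every time: the added alpha is P(Bin(20, 0.40) = 8) × P(Bin(41, 0.40) ≥ 23) = 0.1797 × 0.0270 = 0.0049. Total 0.0487 + 0.0049 = 0.0536, which is the most this override can produce.

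**Step 3: how many are scanned when the 20th patient is recruited?** Assume even accrual of 61 patients and dosing at recruitment. Spacing is months × 30.44 / 61 days. Patient i started (20 − i) × spacing days before patient 20 and must have reached 56 days.

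| Accrual, months | Spacing, days | 56 / spacing | Patients scanned |
|---|---|---|---|
| 10 | 4.99 | 11.2 | 8 |
| 11 | 5.49 | 10.2 | 9 |
| 12 | 5.99 | 9.4 | 10 |

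Using 49 or 63 days for the scan window widens the range to 7 to 11.

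**Step 4: error rates of such a look.** The documents give no boundary for m < 20. Assume it is scaled to 40% of those assessed, so stop at r = floor(0.4m), with the final rule unchanged:

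P(reject | p) = sum over x > r of P(Bin(m, p) = x) × P(Bin(61 − m, p) ≥ 31 − x).

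| m assessed | Stop at | False stop at 60% | Power | Alpha |
|---|---|---|---|---|
| 8 | ≤ 3 | 0.174 | 0.794 | 0.040 |
| 9 | ≤ 3 | 0.099 | 0.861 | 0.046 |
| 10 | ≤ 4 | 0.166 | 0.802 | 0.040 |
| 20 | ≤ 8 | 0.057 | 0.904 | 0.049 |

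An early look on this rule costs power and does not raise alpha.

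**The case against.** **Intent.** Both stopping-rule sections count responders out of 20, and the other sections speak of responders observed in the stage. Protocol 3.2 describes enrolling and treating the stage 1 patients through C8D1 before it states the stop. *Once* can mark a precondition rather than a date. This stands: a reader might infer that an early look was planned, and the documents do not support that. What remains is that the only sentence timing the review names recruitment and no assessment.

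**Committee language.** Protocol 3.3 makes the DRC a body that gives recommendations, so that verb is natural. The conflict lies in *may*. Seven other statements do supply the outcome at 8 or fewer, so a reader of the whole protocol knows that termination was intended. The two stopping-rule sections read alone do not say what follows if no recommendation is made.

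**Size.** An alpha of 0.0565 needs the stop to be ignored at every count, which is extreme. The 79 to 86% depends on an assumed boundary, and rounding makes power move unevenly with m. At half the planned accrual rate, 14 or 15 patients would be assessed, with power 0.900 or 0.869. These limits stand too.

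**A tempting overstatement.** A reader might conclude that 90% power requires all 20 to be assessed. It does not: on the scaled boundary, 16 assessed (stop at 6 or fewer) gives power 0.901 with alpha 0.0490, and 18 (stop at 7 or fewer) gives 0.902 with 0.0488. Nor should one count unscanned patients as non-responders against the boundary of 8, which would stop almost any drug. Protocol 8.1 and SAP 10.5.1 treat only patients with a post-treatment evaluation as evaluable for response.

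**Conclusion.** The inconsistency is real and minor. The stated alpha and power are correct for a binding stop with the 20 stage 1 patients assessed. The two stopping-rule sections make the stop optional and attach it to recruitment. Making it optional moves alpha from 0.0487 to at most 0.0536 for an override at exactly 8 of 20, and to 0.0565 if the stop is never applied. Taking the timing literally would leave about 8 to 10 of 20 patients scanned and power of about 79 to 86%. Those two ranges rest on even accrual over 10 to 12 months, dosing at recruitment and a boundary scaled to 40%, none of which the documents specify.

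A reader might infer that the type I error of this trial was inflated. It was not: the notes in SAP 5.1 record closure after stage 1 and no stage 2, so the final test will not be run and no remaining test changes. The point concerns the design as written.

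**What to change.** Reword the efficacy bullet identically in Protocol 3.7 and SAP 5.1 so that it agrees with Protocol 9.2:

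*When all 20 stage 1 patients have had their stage 1 response assessment or have discontinued, the DRC reviews efficacy; if 8 or fewer have responded, the study will be terminated, otherwise 41 more are enrolled.*

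The sponsor should name the assessment. Stage 2 may open as soon as the ninth responder among the 20 is documented. The error rates are unchanged, because that is the same event as passing the boundary.

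The text cost is one sentence in each document; no patients are added and both boundaries stay. The possible cost is time, if accrual pauses while the last stage 1 patients reach the named visit. The synopsis allows 10 to 12 months plus 7.5, or 17.5 to 19.5 months, and says "Estimated clinical duration is about 20 months". A full pause to C3D1 is 56 / 30.44 = 1.8 months, giving 19.3 to 21.3. C5D1 adds 3.7 months (21.2 to 23.2) and C8D1 adds 6.4 (23.9 to 25.9). Opening stage 2 at the ninth responder shortens the pause when the drug is active. An earlier visit shortens it too, but leaves later responders out of the count at the look, and the sponsor should weigh that when naming the visit.

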4 SELECTION AND WITHDRAWAL OF SUBJECTS

4.1 Inclusion Criteria

Patients must meet all the following inclusion criteria to be eligible for participation in this study:

- 1. Patients with diagnosis of B-cell CLL as confirmed by histopathology or flow cytometry.
- 2. Disease status defined as refractory to or relapsed after at least one prior therapy.
- 3. Presence of measurable lymphadenopathy, defined as the presence of ≥ 1 nodal lesion that measures ≥ 1.5 cm in the longest diameter (LD) as assessed by computed tomography (CT).
- 4. ECOG performance status ≤ 2 .
- 5. Male or female ≥ 18 years of age.
- 6. Life expectancy of at least 3 months.
- 7. Adequate bone marrow (BM), liver, and renal function as assessed by the following laboratory requirements conducted within 14 calendar days before starting study treatment.
 - a. Adequate bone marrow function:
 - I. Haemoglobin ≥ 9 g/dl
 - II. Absolute neutrophil count (ANC) $\geq 1 \times 10^{9}/L$
 - III. Platelets $>50 \times 10^{9}/L$

Patients with hemoglobin, neutrophil and platelet counts below the above specified values will be eligible if it is due to tumor dissemination or infiltration to bone marrow and as per physician's discretion. Hemoglobin and platelet requirements should not be met by use of recent transfusion or growth factor support (G-CSF or erythropoietin) within 3 weeks prior to assessment.

- b. Adequate liver function:
 - I. Total bilirubin ≤ 1.5 times the upper limit of normal (ULN)
 - II. ALT and AST should be ≤ 3 x ULN. ALT and AST ≤ 5 x ULN if known liver involvement.
- c. Adequate renal function: Calculated creatinine clearance ≥ 50 mL/min (as calculated by the Cockcroft-Gault method) or Creatinine ≤ 1.5 mg/dl.
- 8. Ability to swallow and retain oral medication.
- 9. Female patients who are not of child-bearing potential, and female patients of child-bearing potential should have a negative serum pregnancy test within 3 days prior to Cycle 1 Day 1 (C1D1). Female patients of child-bearing potential must consent to use a medically acceptable method of contraception as defined in *Appendix A*, throughout the study period and for 30 days after the last dose of study drug.

Protocol No: RP6530-1901 Version: 1.0, Dated 12 September 2019

- 10. Male patients willing to use adequate contraceptive measures throughout the study period and for 12 weeks after the last dose of Tenalisib.
- 11. Willingness and ability to comply with trial and follow-up procedures and give written informed consent.

